APPENDIX A - SAMPLE SIZE AND RATIONALE

A. Overview

The primary objective of this study is to evaluate the effectiveness of beta-blocker therapy in reducing all cause mortality in patients with moderate to severe congestive heart failure who are receiving concomitant optimal medical therapy. The study is planned as a double-blind, two-arm clinical trial of NYHA class III-IV patients with ejection fraction ≤ 0.35 randomized to either the placebo or beta-blocker (bucindolol) groups. The primary endpoint is time to death. We estimate that 2800 patients will be required to detect with 85% power a 25% annual mortality reduction with bucindolol therapy, taking into account several factors that tend to reduce power. Our approach to sample size was a) to calculate the required number of patients for a range of reasonable design assumptions; b) decide on a sample size; and c) carry out a sensitivity analysis for the fixed sample size in order to evaluate the impact of misspecification of assumptions on the power of the trial.

While there are many approaches to calculating sample size for time-to-event data, the method of Lakatos^{81, 82} was used because it provides estimates of sample size for tests based on the logrank statistic after adjusting for complex trial characteristics such as staggered accrual, time-varying hazard ratios, a lag in treatment effect, losses to followup, noncompliance, and heart transplantation. The adjustment is accomplished by assuming a placebo death rate and percent mortality reduction with treatment (or equivalently a hazard reduction) in a "perfect" trial and then adjusting the rates based on a schedule over time of losses, noncompliance, etc. The observed mortality reduction after adjustment will be lower than before adjustment.

Although randomization will be stratified by hospital site, presence/absence of coronary artery disease, ejection fraction, race and gender, we did not incorporate stratification in the sample size calculations and instead assumed average rates across strata.

B. Assumptions

The target sample size of 2800 patients (1400 per group) was based on the following assumptions (annual rates for mortality, losses to follow-up, noncompliance, and heart transplantation refer to patient years on study, not calendar time):

- 1. Significance level (Type I error) of 5%, two-sided
- 2. **Power** (sensitivity) of 85%
- 3. **Patient accrual** assumed to be uniform over a 3 year intake period, 18 month minimum followup, 3 year average followup, total study length of 4.5 years.
- 4. Annual mortality rate of 15% in the placebo group (prior to adjusting for noncompliance, losses etc.) which is conservative based on similar previous studies of heart failure^{5,6,8,9,63}. These studies are summarized in the table below, with our proposed study BEST as the last entry.

Study	Severity of Heart Failure	Mortality Rate	
VA V-HeFT II ⁸ enalapril group	NYHA class II & III with <1% class IV	16.5% annually	
SOLVD ⁶ enalapril group	mild to moderate	12% year 1 10% year 2 13% year 3 7% year 4	
CONSENSUS ⁵ enalapril group	severe, NYHA class IV	36% year 1	
PROMISE ⁶³	moderate to severe (all patients) NYHA class III NYHA class IV	32% year 1 27% year 1 40% year 1	
BEST (proposal)	moderate to severe $EF \le 35$, NYHA class III-IV	15% annually	

(The rates shown for SOLVD are approximations estimated from the cumulative rates extrapolated from Kaplan-Meier curves).

Patients in PROMISE had a high mortality rate despite angiotensin converting enzyme inhibitors. However, PROMISE randomized patients to inotropic therapy and therefore only the sickest patients were entered. Due to some investigator bias against randomizing the sickest patients to a beta-adrenergic blocking agent, a conservative annual placebo group mortality of 15% is assumed in the proposed study.

- 5. **Mortality reduction** The study target is set for detecting a reduction in annual mortality of 25%, i.e. from 15% to 11.25% before adjusting for losses, noncompliance, etc. The design implications of these factors are discussed below. The planning committee decided that a 25% reduction in annual mortality under ideal experimental conditions was the smallest effect size of clinical interest upon which they were willing to base the trial. It is estimated below that the adjusted cumulative 4.5 year mortality rates would be 35% and 30% in the placebo and beta-blocker groups, respectively, which results in an adjusted cumulative 4.5 year mortality reduction of 15%. The need for adjustment is due to the following complicating assumptions.
- Lag An initial 3 month lag in treatment benefit is assumed (i.e., death rates in the two groups were assumed to be equal during the initial 3 months of patient follow-up) since 5-9 weeks are needed to titrate patients onto bucindolol.
- 7. Loss-to-followup An annual rate of ~1% or cumulative rate of 5% in each treatment group. A loss is defined to be a patient who at some point during the study can no longer be observed for the occurrence of death. Survival status in the VA can be ascertained with almost 100% accuracy through the VA Beneficiary Identification and Record Locator Subsystem (BIRLS).
- 8. Noncompliance The projected annual rate of noncompliance (i.e. permanent discontinuation) in the bucindolol group of 10% in year 1 and 2% per year for the next 3.5 years. This is approximately a 16% cumulative rate, which is conservative based on the experience with the drug ^{3,26,27,30,31,43} but reasonable in a large multi-center clinical trial. The assumed rates are 'front-loaded' to reflect higher anticipated rates of noncompliance and intolerance early in patient followup. In accordance with the

intention-to-treat principle, outcomes of noncompliant patients are counted in the treatment group, to which they were randomized. Noncompliance is expected to diminish the mortality reduction achieved with therapy because patients will be off drug. (When noncompliers go off therapy they are assigned placebo death rates in sample size calculations.)

- Drop-in rate (i.e. patients assigned to placebo but taking bucindolol) was assumed to be 0% since it is rare for heart failure patients to be placed on beta-blocker therapy.
- 10. **Heart transplantation rates** of 1.85% per year in the placebo group and .37% in the bucindolol group, beginning in year 2 of patient followup. This is based on a projected study population composed of the following proportions of patients: 50:50 VA:NIH, 40:60 women:men, 1% per year transplant rate in NIH women (older population not transplant eligible), 3% per year transplant rate in NIH men, and 1.5% per year transplant rate in VA men. The differential group transplantation rates reflect those in the MDC trial³⁵, 9% cumulative rate in the placebo group and 1% cumulative rate in the beta-blocker (metoprolol) group. Because the rate of transplantation in women and in the VA system is far less than that in the MDC participating centers, we expect lower rates during this trial. Transplants are assumed to occur after year 1 because patients on a transplant list or anticipated to be on a list within the 6 months following randomization are excluded from entering the study and are unlikely to have a transplant during year 1 of followup. Although we discourage patients who will be considered for transplant from being randomized, we cannot ethically exclude these patients from transplant after they have entered the trial. Because transplantation may not be random, censoring patients at time of transplantation could introduce a bias. Rather than censoring at transplant, we decided that post-transplant survival should accrue to the randomized treatment (intention-to-treat principle). We adjusted mortality rates in sample size calculations making the assumption that 80% of patients receiving transplants would have died within a year if they not received their transplants. This lowered the expected mortality rate preferentially in the placebo group and had the net effect of diminishing the observed mortality reduction.

11. AICD The sample size was not adjusted for the use of automatic implantable defibrillators (AICD). These devices are permitted by protocol but currently about 1% of heart failure patients receive these devices annually. We also do not have evidence for a differential implantation rate between treatment groups. Under the assumption that half of the deaths will be due to progressive heart failure and half to sudden death and that use of AICD will not diminish death due to progressive heart failure, then at most 0.5% of each group may have prolonged survival. This would lower the mortality rate in the two groups, but by an equal and negligible amount.

Power	Noncompliance	# deaths	Sample Size
80%	10% yr 1, 2% per yr 2+ ~ 16% cum	799	2433
	15% yr 1, 4% per yr 2+ ~ ~ 25% cum	908	2754
85%	10% yr 1, 2% per yr 2+ $\sim 16\%$ cum	916	2790
	15% yr 1, 4% per yr 2+ $\sim 25\%$ cum	1041	3157
90%	10% yr 1, 2% per yr 2+ $\sim 16\%$ cum	1068	3254
	15% yr 1, 4% per yr 2+ ~ 25% cum	1215	3683

 Table 1. Sample Size for Joint VA-NHLBI Trial

Assumptions: two-sided .05 level, uniform entry, 15% per year placebo event rate, 11.25% per year bucindolol event rate, 25% unadjusted annual mortality reduction, 3 month lag in treatment effect, 1% per year loss to followup, front-loaded noncompliance, 0% drop-ins, 3 year intake, 4.5 year trial, intention to treat;

Heart transplantation rates for joint trial are 1.85% in the placebo group and .37% in the bucindolol group. These rates assume -- 50:50 VA:NIH, 40:60 women:men, 1% per year transplants in NIH women (older population not transplant eligible), 3% per year heart transplants in NIH men, 1.5% per year transplants in VA men. (Lakatos method).

All annual rates given in terms of patient follow-up time not calendar time. Sample size of 2790 patients for the trial (shaded cell) is rounded up to 2800.

C. Sensitivity Analysis

Table 3.1 shows the pattern of sample sizes as power and noncompliance rates vary. Approximately, a 5% increment in power results in a 15% larger sample (350-450 patients). Also, there is approximately an increase of 13% (325-425 patients) as the cumulative noncompliance increases from 16% to 25%. The shaded cell in the table shows the projected sample size of about 2800 for this trial.

Using the method of Lakatos,^{81, 82} Figures 3.1-3.4 were constructed to show trends in the sensitivity of the trial as we fix the sample size at the targeted 2800 patients, make the design assumptions described above, and then vary these assumptions.

Figure 3.1 shows an acceptable loss in power (85% to 81%) if beta-blocker noncompliance is twice as high as projected (~16% vs 25% cumulative).

Figure 3.2 illustrates the loss in power with a lag in the treatment effect. This loss is expected since the sample size is driven by the number of deaths observed, which will be reduced by about 1/12 with a 3 month lag. The trial was sized for a 3 month lag based on the conservative assumption that patients will not obtain any benefit of therapy for three months because of the initial 5-9 week titration period. If the lag is 6 months instead of 3 months then power is reduced from 85% to 72%. The study investigators against using the more conservative 6 month lag in designing the trial since such a long delay in therapeutic benefit is not anticipated.

transplantation rates in

the range of interest effect the power of the trial. The study investigators assumed the higher placebo transplant rate of 1.85% and bucindolol transplant rate of .37% per year after year 1 in calculating our target sample size (see Table 1 in this section). Power is reduced from 96% to 85% as transplantation rates range from 0% to 1.85% per year in the placebo group when the cumulative noncompliance is 16%. We also assumed that 80% of patients receiving transplants would have died within a year if the transplantations had not been performed. If we increment this death rate among transplant patients from 50 to 80 to 100% the power decreases about 5% or less with each increment, as shown in Figure 3.3b. Sensitivity differences were about 5% or less as the level of noncompliance increased in Figures 3.3a and 3.3b.

Figure 3.4 is included to show that placebo mortality rates and percent mortality reduction have pronounced effects on the sensitivity of the trial. By comparison, misspecification of the noncompliance rate has a much smaller effect. If the noncompliance rate is 16% and percent reduction with treatment is 25% as assumed for this trial, and if the unadjusted placebo rate is an unexpectedly low 10%, then power is reduced to 57%. Because the projected placebo mortality rate of 15% is considered conservative in a population of moderate to severe heart failure patients, we show that a higher mortality rate of 20%, which may be obtained, offers some protection against misspecification of other assumptions. If the mortality reduction is 20% versus the desired 25% and the noncompliance is 16% with a placebo mortality rate of 15% then the power of the trial is reduced to 60%. The study investigators chose 25% to be the effect size of clinical interest in designing this trial.

D. Study Duration

This study is planned for a total duration of 4.5 years in 90 medical centers. Three years will be needed to recruit 2800 patients at an average rate of approximately 1 patient per month per center. A minimum followup of 18 months was considered necessary to observe the effects of bucindolol. Other smaller studies previously discussed have shown therapeutic benefit within this period of time. Other combinations of intake period and study duration were considered such as a shorter trial with more centers and a longer trial with fewer centers, but the advantages did not appear to outweigh the disadvantages in terms of complexity and cost.

E. Contingency Plans

If the cumulative mortality rate in the control group is substantially lower than expected by the end of the second year of the study, the sample size may have to be increased and/or follow-up extended to observe a sufficient number of deaths, or the need for a study reevaluated in the light of the low control mortality.

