d) quality control, and e) clinical performance data at each center. Special attention will be paid to the recruitment of participants (especially women) during that phase of the study and maintaining high adherence. These quarterly reports will include summaries of the Clinical Center progress on patient screening as well as relevant statistics from the screening and randomization visits. If required, the data can be transmitted via telephone lines. No endpoint or side effect data will be included in the Steering Committee Reports.

3. Data and Safety Monitoring Board Reports

The Data and Safety Monitoring Board reports will be prepared twice a year. These will be tailored to meet the needs of the committee. The report will consist of six major sections: **a**) General Progress of Study and Recruitment, **b**) Endpoints, **c**) Possible Toxicity and Side Effects, **d**) Adherence, **e**) Data Quality, and **f**) Substudies. The General Section will outline participant recruitment and effective patient-years of follow-up in comparison to targets stated in advance. The section on endpoints will contain treatment comparisons with respect to both the major outcome of mortality and the secondary outcomes of this protocol. The Quality of Life section will compare the two groups with respect to the quality of life questionnaire. The Possible Toxicity and Side Effects section will compare the treatments with respect to hospitalizations, specified clinical chemistries, and

other measures of side effects. Adherence to study medications and comparisons of observed versus projected measures will be reported in the fifth section. This will include reports of the average pill count in the treatment groups and other measures of adherence. The sixth section will contain quality control reports which will aid the committee in evaluating the data of the preceding sections. In each of these sections, data will be provided for the study as a whole and separately for each clinic.

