The primary objective of this study is to determine whether treatment with beta-adrenergic blockade compared to placebo reduces all cause mortality in patients with moderate to severe congestive heart failure who are concurrently receiving optimal medical therapy. The null hypothesis to be tested is that there is no difference in survival time between active and placebo arms.

Two-tailed treatment comparisons will be made by the nonparametric logrank statistic with the exact variance calculation stratified by site, presence/absence of CAD and gender. This statistic is the optimal nonparametric test when censoring is equal in the treatment groups under proportional hazards. The analysis will include all survival times for all randomized patients in the treatment group to which the patient had originally been assigned (intention-to-treat principle). Significance levels will be set in accordance with the plan for monitoring the study.

Cumulative survival curves will be constructed by Kaplan-Meier methods.⁷⁹ The Cox life table regression method⁸⁰ will also be used to calculate estimates of relative risk, provided the model fits the data.

3. Secondary Objectives

Treatment differences will be evaluated in cause-specific cardiovascular mortality: total cardiovascular mortality, sudden death, worsening congestive heart failure, and ischemic cardiac events. These outcomes will be classified by the Mortality Committee which will remain blinded to treatment assignment. Cause-specific mortality will be further examined to estimate if treatment effect is similar for the different causes of death. Also, the cost of the two therapies will be examined.

The frequency of adverse effects in each treatment group will be analyzed using the chi-square statistic.

4. Subgroup analyses

All prior subgroup hypotheses related to treatment effect modification will be examined with tests to detect significant interactions. Our clinical interest focuses on qualitative interactions. We will use appropriate methods such as Cox regression⁸⁰ and stratified Kaplan-Meier curves.⁷⁹ However, the power to detect differences in treatment effects among subgroups will generally be lower than the power to detect an overall treatment effect. If tests of interaction are significant, then estimates of treatment effect will be derived within each subgroup. All reports of differences based on data-derived subgroups will be identified as such.

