The following subgroups will be included in analyses to evaluate the effect of beta-adrenergic blocking agents on all cause mortality

- 1. Presence or absence of coronary artery disease.
- 2. Gender
- 3. Race
- 4. Age
- 5. Baseline left ventricular ejection fraction.
- 6. Baseline serum sodium concentration.
- 7. Baseline NYHA functional class.
- 8. Baseline plasma norepinephrine.
- 9. Baseline heart rate.
- 10. Baseline heart rhythm (sinus rhythm versus atrial fibrillation).
- 11. Baseline systolic blood pressure.
- 12. Improvement in left ventricular ejection fraction from baseline to 3 months of therapy.
- 13. VA versus non-VA site, after adjusting as far as possible for clinical prognosis.

5. Other analyses

Additional analyses for treatment group effects will include as outcome variables:

- a. Hospitalizations per month of life
- b. Quality of life indicators

c. Incidence of myocardial infarction

d. Left ventricular ejection fraction at 3 and 12 months of therapy.

As beta-adrenergic blockade has been shown to improve ventricular function in patients with congestive heart failure, examination of changes in left ventricular ejection fraction in the bucindolol group will be compared to the placebo group. Analyses will include examination of the response of patients (i.e. change in left ventricular ejection fraction) with regard to baseline norepinephrine levels, baseline heart rate, baseline ejection fraction, baseline systolic pressure and presence or absence of coronary artery disease, to determine which group will have the most favorable hemodynamic response to beta-adrenergic blockade.

C. Interim analysis

Interim monitoring will focus on patient intake (overall and within hospital), hospital adherence to protocol, adverse reactions, baseline comparability of treatment groups and effect of treatment on the primary study outcome.

Due to ethical considerations, the study will be reviewed by the DSMB which may recommend early termination of the trial based on interim analyses. The DSMB will use a Lan-DeMets upper boundary with an intermediate spending function, and stochastic curtailment for the lower boundary.

IX. Data Collection and Management

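### Appendix A's 85% power is for a single fixed 5% test and leaves out the interim boundaries that the protocol adopts; its 81% noncompliance figure is not for a doubling

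*Protocol*

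**What the plan says.** Appendix A, Overview, gives the headline: "We estimate that 2800 patients will be required to detect with 85% power a 25% annual mortality reduction with bucindolol therapy". It sizes the trial on one error rate, "Significance level (Type I error) of 5%, two-sided", and Table 1 repeats it: "two-sided .05 level, uniform entry, 15% per year placebo event rate, 11.25% per year bucindolol event rate, 25% unadjusted annual mortality reduction". The design row reads 916 deaths and 2790 patients, rounded up to 2800. The Overview says several power-reducing factors are taken into account. The list that follows covers treatment lag, loss to follow-up, noncompliance and transplantation. It explains why defibrillators are not adjusted for, and the Overview says that stratification was left out. Monitoring is not mentioned.

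Section VIII.C says: "The DSMB will use a Lan-DeMets upper boundary with an intermediate spending function, and stochastic curtailment for the lower boundary". Section VIII.B.2 says of the primary test: "Significance levels will be set in accordance with the plan for monitoring the study". Section VIII.A.3 says "The Data and Safety Monitoring Board reports will be prepared twice a year", with treatment comparisons on mortality in each report. Section III.B has the board meeting at least once a year.

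Section II.D notes that accrual was extended by 7 months, and the preface adds that follow-up was extended to match. Appendix A still describes 3 years of intake and 4.5 years in total.

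On sensitivity, Appendix A.C reports an "acceptable loss in power (85% to 81%) if beta-blocker noncompliance is twice as high as projected (~16% vs 25% cumulative".

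**The concern.** A test that spends part of its 5% at interim looks needs a final critical value above 1.96. At a fixed number of deaths this lowers power. A futility rule that is followed lowers it again, because some trials that would have reached significance are ended early. If 85% was computed without either boundary, the protocol's power statement describes a different test from the one it plans.

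The noncompliance sentence is a separate matter in the same appendix. It presents a 4-point loss as the price of doubling noncompliance, but its own percentages are not in the ratio of two. The robustness margin that it calls acceptable would then be overstated.

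**Working it through.** **1. Reproduce the plan's figure.** Inputs, all from Appendix A: 15% and 11.25% annual mortality; 3-month lag; 1% per year loss; bucindolol noncompliance of 10% in year 1, then 2% per year, with noncompliers at placebo rates; transplant rates of 1.85% and 0.37% per year from year 2, with 80% of those patients otherwise dying; uniform entry over 3 years; 4.5 years in total. Annual rates become hazards by −ln(1 − rate), and death rates are lowered by 0.8 × the transplant rate from year 2. A Lakatos-type logrank calculation with one test at z = 1.96 gives:

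| Noncompliance | Power | Patients, rebuilt | Patients, Table 1 |
|---|---|---|---|
| 10% / 2% | 80% | 2436 | 2433 |
| 10% / 2% | 85% | 2787 | 2790 |
| 10% / 2% | 90% | 3262 | 3254 |
| 15% / 4% | 80% | 2758 | 2754 |
| 15% / 4% | 85% | 3154 | 3157 |
| 15% / 4% | 90% | 3692 | 3683 |

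The design row has 914 deaths rebuilt, against 916 stated.

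**2. Look for a hidden allowance.** For a fixed test, deaths are proportional to (1.960 + z_power)². At 80, 85 and 90% power this is 7.849, 8.978 and 10.507, so the ratios to 80% are 1.144 and 1.339. Table 1 gives 916/799 = 1.146 and 1068/799 = 1.337. The table is a plain 1.96 test with no monitoring allowance.

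**3. Add the boundaries, 4.5-year design.** The drift at 2800 patients is (1.960 + 1.036) × √(2800/2790) = 3.002. At information fraction t, Z(t) is normal with mean 3.002√t. Assumptions, because the protocol does not fix them:

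- Intermediate spending is taken as 0.025·t^ρ, one-sided in the direction of benefit, with ρ = 1, 1.5 or 2.
- Looks are yearly plus final (5) or half-yearly (9). Information comes from the modelled deaths: about 2% at six months and about a quarter at two years.
- Curtailment applies when conditional power under the design effect is below 0.10 or 0.20, and is always followed.

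| Spending | Looks | Final z | Upper boundary only | With CP < 0.10 | With CP < 0.20 |
|---|---|---|---|---|---|
| α·t² | 5 | 2.126 | 83.0% | 82.8% | 82.2% |
| α·t² | 9 | 2.144 | 82.7% | 82.3% | 81.4% |
| α·t^1.5 | 5 | 2.187 | 82.0% | 81.7% | 81.1% |
| α·t^1.5 | 9 | 2.209 | 81.5% | 81.1% | 80.1% |
| α·t | 5 | 2.287 | 80.1% | 79.8% | 79.0% |
| α·t | 9 | 2.316 | 79.4% | 78.8% | 77.6% |

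The final two-sided nominal level is about 0.020 to 0.033. Keeping 85% with the upper boundary alone would take about 971 to 1062 deaths. As an outer reference, O'Brien-Fleming-type spending alone gives about 84%.

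**4. Add the 7-month extension.** Assume uniform accrual of 2800 patients over 43 months and 61 months in total. The modelled death proportion rises from 0.3281 to 0.3507, which is 2800 × 0.3507 = 982 deaths. The drift becomes 3.002 × √(0.3507/0.3281) = 3.104, and fixed-test power is Φ(3.104 − 1.960) = 87%. With the same spending functions (6 or 11 looks), power is 82–85% for the upper boundary alone, 81–85% with curtailment below 0.10, and 79–84% with curtailment below 0.20.

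**5. The noncompliance sentence.** 25/16 = 1.56. Table 1 shows that row as 15% in year 1 and 4% per year after, against 10% and 2%: year 1 rises 1.5-fold and only the later rate doubles. Rebuilt fixed-test power there is 80.6%, which matches the stated 81%. A true doubling is 20% and 4%, cumulatively 1 − 0.80 × 0.96^3.5 = 31%. The rebuilt fixed-test power is then about 76–77%.

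**The case against.** The spending function, the number of looks and the curtailment threshold commonly sit in an analysis plan or a board charter, so their absence here is no defect. That stands, and the point does not rest on it. The protocol itself commits to the boundaries and itself prints a power that ignores them.

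It is also fair that any single range rests on assumptions. Half-yearly reports need not be nine formal looks, since the board must meet only yearly, and spending close to O'Brien-Fleming would cost only about one point. The direction is certain; the size is not.

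The strongest objection is the extension. On the assumed schedule, about 982 deaths exceeds the 971 needed at the mild end, so the protocol as it now runs may have 85% after all. A reader might infer from the 4.5-year figures that the trial is underpowered, or that its power simply is 79–83%. The documents do not support either statement. Nor is there any suggestion of an inflated type I error, because section VIII.B.2 ties the final level to the monitoring plan.

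On noncompliance, the sentence prints 16% and 25% beside the wording, and 81% is right for that scenario. The error is in the description, but it makes the design look more robust to a doubling than it is.

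**Conclusion.** The point holds in this form. Appendix A's 85% at 2790 patients and 916 deaths over 4.5 years is the power of one fixed two-sided 5% test. It carries no allowance for the monitoring boundaries in section VIII.C. For spending between α·t and α·t² and 5 to 9 looks, the shortfall on that schedule is about 2 to 6 points for the upper boundary alone. It is about 3 to 7 points if curtailment below 0.20 is followed.

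The extension may recover part or all of this, provided that it adds follow-up for all 2800 patients at uniform accrual. Appendix A does not say, because it was not updated. The 81% figure belongs to noncompliance about 1.6 times the projection; a true doubling costs roughly twice the stated loss.

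**What to change.** - Restate in Appendix A, and where section II.D repeats it, the power at 2800 patients under the monitoring boundaries actually adopted, for both the 4.5-year and the extended schedule. Alternatively, label the 85% as fixed-sample power before monitoring.
- In Appendix A.C, describe the 81% scenario as noncompliance about 1.6 times as high (15% in year 1 and 4% per year, against 10% and 2%). Add that a true doubling (20% and 4% per year, about 31% cumulative) gives about 76–77% fixed-test power.

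The cost is a recalculation, a few sentences and possibly a slightly less favourable stated power. Neither the sample size nor the boundaries need to change.
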